#### **Optional Additional Study Visit after Treatment is Complete**

Participants will be given the option to participate in an additional study visit that occurs after they have completed 12 months on study drug. Participants will return 6 weeks after the 12-month visit. The purpose of this visit is to examine how vascular function, laboratory and urine markers change after being off the study medication for 6 weeks. This visit will last approximately 1.5 hours and the following will occur:

- Vital signs, history and physical examination including medication history.
- IV catheter will be placed and blood will be collected to measure a basic metabolic panel and venous blood gas
- Additional blood will be collected to examine inflammatory markers to see if changes persist after discontinuing treatment
- Participants will return a 24-hour urine collection. This sample will be used to measure 24-hour urine electrolytes, ammonium, pH, creatinine, and urea nitrogen.
- Vascular endothelial function will be measured as described above.

Participants will not be on study medication during this 6-week period. The only risk associated with this visit includes the blood draw and the use of nitroglycerin for measurement of vascular function. Participants will be given the option to consent for this additional study visit. They will receive \$25 if they complete this visit.

#### **Protection of Human Subjects**

**Sources of Research Material:** This is a prospective study of newly recruited human subjects with CKD stage 3-4. The data collected will be used exclusively for research purposes. All subject identities and records will remain strictly confidential. We will obtain brachial artery flow mediated dilation, aortic pulse wave velocity, and left ventricular mass measurements, blood samples and demographic and clinical data, including detailed medical and medication histories.

**c) Potential Risks:** We see no psychological, social, or legal risks beyond those of participation in health related research in general. The potential physical risks of participating in the proposed experiments are reasonably small. The procedures have been used previously by the team of investigators without

complications. Importantly, all of the procedures will be performed in the Clinical Vascular Physiology Laboratory at the University of Colorado Denver and in the Brain Imaging Center MRI lab at University of Colorado Denver, both of which have on-site full-time physician supervision, nursing, and other clinical and research support personnel, safety equipment and established emergency procedures. Moreover, a Data Safety Monitoring Board (DSMB) will be appointed to oversee this ancillary study.

The risks associated with the experimental protocols include:

- **Venous catheter:** discomfort associated with insertion of the needle; local bleeding and a small hematoma (~10% of cases); risk of infection of a hematoma or significant external blood loss (<1 in 1000), risk of fainting. Subjects with CKD may have plans in place for future vascular access for hemodialysis and thus we will place the venous catheter in the arm not designated for future vascular access.
- **Endothelium Dependent Dilation (FMD):** inflating the blood pressure cuff below the elbow during this procedure may cause a mild to moderate intensity “pins and needles or numbing” sensation that goes away as soon as the cuff is deflated. Since CKD patients may need future vascular access for hemodialysis, the FMD measurement will be done in the arm not designated for future vascular access for dialysis.
- **Endothelium Independent Dilation (EID):** Sublingual Nitroglycerin is used to determine EID. Nitroglycerin may cause a slight decrease in arterial blood pressure. The subject may experience minor symptoms such as lightheadedness, tingling in the tongue and in the arms and legs, light headaches, fainting and/or increased heart rate. Nitroglycerin will not be given to any subject with a systolic blood pressure less than 100 mm Hg and/or heart rate <60 or >100 on the day the measurements are performed. The dose of Nitroglycerin used is considered safe and is used in patient populations to relieve angina.
- **Magnetic Resonance Imaging:** The risk of performing cardiac MRI is minimal. The magnetic field generated within the MRI is not harmful but can cause metal within the body to heat up or electronics to stop working. All subjects will be questioned regarding the presence of metal or electronic devices inside their body (e.g. pacemakers, etc). All subjects with either metal implants or implanted electronic devices will be excluded from the study. As the MRI is a small round tube, it may make subjects who experience claustrophobia uncomfortable. Thus, all consenting subjects who experience non-severe claustrophobia will be asked to have their private physician prescribe a suitable medication to control their anxiety associated with the procedure. These subjects will be instructed to bring a designated driver with them to the MRI visit. The most common minor side effect of having a MRI exam is flashing lights in the eyes. This is caused by the magnetic waves and is not harmful. Some people also experience warmth and reddening of the skin, which usually goes away after a few minutes. For all female participants of childbearing age, a pregnancy test prior to MRI will be required. All scans will be performed without gadolinium given the risk of nephrogenic systemic fibrosis in patients with CKD.
- **Medications:** With any medication used in testing, there is small risk of an allergic reaction. Reactions reported with the use of the specific medications proposed for use include:
  - **Sodium bicarbonate** is an FDA approved medication for the treatment of metabolic acidosis and as an antacid. It is extremely well tolerated. The main side effect of oral sodium bicarbonate is flatulence and gastric distension. Metabolic alkalosis and weight gain from water retention can also occur but are rare. Serious reactions are uncommon with oral administration of the drug but include edema, CHF exacerbation, hypertension, hypernatremia, hypokalemia and pulmonary edema. Patients will be monitored monthly for side effects (see data and safety monitoring plan below).
  - **Nitroglycerin** may cause a slight decrease in arterial blood pressure, minor symptoms such as lightheadedness, tingling in the tongue and in the arms and legs, headaches, fainting and/or increased heart rate. The dose of nitroglycerin used is considered safe in the proposed population and is also used in patient populations to relieve angina.

There are no alternative methods that would provide the same type and accuracy of information as the state of-the art procedures proposed in this application.

## **2. Adequacy of Protection Against Risks**

**a) Recruitment and Informed Consent:** We will use the recruitment and adherence strategies and experience previously implemented by the team of investigators as well as the services of the Health Data Compass office. [name] has successfully recruited patients with different etiologies of CKD to clinical trials for several years. Patients for the study will be recruited from nephrology clinics at the University of Colorado Hospital and Denver Health Hospital with access to over 2000 CKD patients.

Written informed consent will be obtained at enrollment using a standardized form approved by the Research Subject Advocate that provides appropriate information about the study and the potential risks and benefits. The subject will then read the consent form and the investigator will answer any questions that the subject may have prior to obtaining the subject's written consent. The consent form will then be signed by both the subject and the investigator as documentation of consent. A copy of the signed consent form will be given to the subject. All of the proposed procedures and protocols will be reviewed and approved by the University of Colorado Institutional Review Board (COMIRB).

**b) Protection against Risk:** To ensure that participants' confidentiality is maintained, each participant will be assigned a unique study identification number and will be tracked through the study by this number. Only the PI and Study Coordinator will maintain the code linking study identification numbers to specific participants. When data generated from any study is shared, only de-identified information will be exchanged. No protected health information will be sent to any collaborators or be used in any publications of the findings.

The potential general risks of the proposed ancillary study measurements will be minimized by:

- Using only safe, well-established procedures, with only qualified and experienced personnel performing the procedures.
- Ensuring constant personal monitoring of each experimental session by the investigators and clinical staff.
- Providing appropriate clinical supervision and emergency equipment and medications
- All blood pressure, blood draws and FMDBA measurements will be performed in the arm not designated for future vascular access for dialysis.
- Risks associated with sublingual Nitroglycerin will be minimized by not administering Nitroglycerin to subjects with systolic blood pressure <100 mm Hg and/or heart rate <60 or >100. During Nitroglycerin administration, heart rate and blood pressure will be monitored every 2 minutes for signs and symptoms of hypotension. Additionally, an intravenous catheter (dorsal aspect of the hand) will be in place for administration of fluid or drugs in the rare event of symptoms due to hypotension or vasovagal bradycardia.
- Safety monitoring by a data safety monitoring board (DSMB)
- Evaluation for adverse events on a monthly basis either through telephone calls or in person visits.

**3. Potential Benefits of the Proposed Research to the Subjects and Others:** Because the risks of participating in this study are relatively small, the risk-to-benefit ratio is relatively small. Subjects will receive benefits associated with overall knowledge of their health from the extensive testing performed for screening purposes and the established subject characteristics (i.e. blood pressure, blood chemistries, etc.). The findings we will generate will answer important questions about bicarbonate administration in patients with CKD and help investigators design future clinical trials in this population. Thus, the new knowledge generated from this proposal will yield potential benefit to CKD patients in general and to society as a whole.

**4. Importance of the Knowledge to be Gained:** The new knowledge generated from this proposal will facilitate planning of future clinical trials in CKD that will aim to reduce the burden of CVD and premature death in this population. In addition, the proposed research should provide important insight into the mechanisms involved in any beneficial effects of bicarbonate administration on vascular function and left ventricular mass in patients with CKD.

**5. Data and Safety Monitoring Plan:** To ensure the safety of subjects, they will need to meet rigorous

inclusion/exclusion criteria, including comprehensive health screening procedures. A data safety monitoring board (DSMB) including clinicians and a statistician (independent of the study investigators but part of the faculty at the University of Colorado School of Medicine) will be formed to assess potential adverse events. The data will be prepared by the DSMB statistician, ensuring the study statistician remains blinded until the final analysis. The DSMB will meet at least 1 time per year to review the protocol and will follow the guidelines established by the NIH National Center for Research Resources, which include: a) monitoring the progress of the protocol (e.g. reviewing subject recruitment, attrition and minority involvement) and the safety of research participants (e.g. reviewing unblinded data for safety); b) assuring compliance with requirements regarding the reporting of adverse events; c) assuring that any action that results in the temporary or permanent suspension of the protocol is reported to all of the appropriate monitoring bodies (IRB, NIH, etc.) and d) assuring data accuracy and protocol compliance. Any unexpected adverse events will be reported immediately to the Colorado Institutional Review Board, the funding I/C and the NIH Office of Biotechnology Activities. This study is not solidly considered as a confirmatory study and as such no interim analysis has been planned.

- **Expected adverse events:** Sodium bicarbonate therapy may cause bloating, flatulence and abdominal discomfort. Although previous studies using similar doses of sodium bicarbonate have not reported significant changes in edema, body weight or BP, sodium bicarbonate may cause edema to develop or worsen thereby increasing BP. Previous studies suggest fluid retention is greater when sodium is accompanied by the chloride anion rather than the bicarbonate anion. As shown in our preliminary data, sodium bicarbonate did not result in increased BP. Sodium bicarbonate also has the potential for causing metabolic alkalosis and hypokalemia if it is retained rather than excreted in the urine. These expected adverse events will be monitored during the course of the study and in general, can be medically managed by adjusting antihypertensive and/or diuretic agents, providing potassium replacement and by dietary changes. Of note, none of these adverse events were observed in our short-term pilot study.
- **Dose reduction and discontinuation:**
  - Serum bicarbonate >26 mEq/L: The intervention dose will be reduced by 50% and diuretics will be adjusted as appropriate. The participant will return for a visit one week later to have serum chemistries rechecked. If the bicarbonate remains >26 mEq/L the intervention will be stopped and the participant will have serum bicarbonate measured weekly until it is <26 mEq/L. Plasma ionized calcium will be checked if bicarbonate is >26 mEq/L at any visit since an increase in pH can decrease the ionized calcium concentration. Management of low ionized calcium will be at the discretion of the PI based on symptoms reported by the patient.
  - Systolic blood pressure ≥ 160 or diastolic blood pressure ≥ 80 mmHg: Potential reasons for uncontrolled BP, such as poor compliance or running out of medications will be evaluated and managed appropriately. If an identifiable cause is not found, the PI will increase anti-hypertensive medications and/or diuretics. The participant will return 1 week later for follow-up. If BP remains >160/80 mmHg at the second visit, medications will again be increased and the intervention dose will be reduced by 50%. The participant will return 1 week later. If BP remains unchanged at the third visit, the intervention will be stopped and medications will again be escalated. Participants will continue to have PRN visits weekly until BP is <160/80 mmHg.
  - Serum potassium < 3.0 mEq/L: The intervention dose will be reduced by 50%, diuretics will be adjusted as appropriate and potassium replacement will be prescribed. The participant will return 1 week later for repeat labs. If serum potassium remains < 3.0 mEq/L, the intervention will be discontinued. The participant will return weekly until serum potassium is > 3.0 mEq/L.
  - Severe edema: If in the opinion of the PI severe edema (4+) is present and another etiology cannot be identified the dose of the intervention will be reduced by 50% and diuretics will be adjusted. If fluid retention remains severe at follow-up visits, the intervention will be discontinued.
  - Rescue therapy with oral sodium bicarbonate: Rescue therapy with open-label sodium bicarbonate will be initiated if serum bicarbonate is <20 mEq/L on 2 consecutive measurements at least 1 week apart since a level <20 mEq/L is associated with adverse outcomes. In this instance, open-labeled sodium bicarbonate will be given to target serum bicarbonate of 20-22 mEq/L. Participants will not discontinue study medications if open-labeled sodium bicarbonate is prescribed.

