- **Run-in:** A 1-month run-in period will occur if patients do not meet the BP goal of  $<140/90$  mmHg. The rationale for this run-in phase is to achieve a stable antihypertensive regimen and BP  $<140/90$  mmHg, such that changes in antihypertensive agents throughout the course of the study are minimal. This will allow for better isolation of the effect of bicarbonate on FMDBA, aPWV and LVMI. During the run-in phase, an up-titration of patients current angiotensin converting enzyme inhibitor or angiotensin receptor blocker to their maximum approved dose or other antihypertensive medication(s) will occur to reach a target BP of  $<140/90$  mmHg by their primary nephrologist or PCP. The duration of the run-in phase will be 4 weeks with weekly visits to achieve the target BP. The PI will contact the primary nephrologist/PCP of the patient if the BP is not at goal and discuss the need for medication changes. A BP  $<140/90$  mmHg is the standard of care for patients with CKD, hence we do not anticipate an issue with the primary nephrologist or PCP making changes to the BP regimen. If the patient is not able to achieve a BP of  $<140/90$  mmHg during this period, the participant will not be included in the study. This overall approach will allow for inclusion of the typical population of patients with CKD 3-4 and increase the generalizability of our expected results.
- **Baseline:** During the baseline phase FMDBA, aPWV, LVMI, serum basic chemistry panel, plasma AII, aldosterone, ET-1, serum T50, venous blood gas, and 24-hour urine collection measurements will be performed in all participants that are able to control their BP as described above.
- **Randomization:** Participants will be randomized with a 1:1 allocation ratio to treatment and placebo group using block randomization. List of randomization will be generated by the study statistician and sent to the study pharmacist (Belmar Pharmacy, Denver, CO) blinded to the PI. Study investigators, healthcare providers, participants, data collectors, outcome adjudicators and data analysts will be blinded to treatment assignment.
- **Follow-up:** The follow-up schedule includes:

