  - 1 month: 1) remote or in-person safety visit (basic chemistry panel, adverse event assessment, gastrointestinal (GI) symptoms questionnaire, BP, pill compliance); 2) optional outcome measures: FMDBA, plasma AII, aldosterone, ET-1, and serum T50. Of note, aPWV will not be measured at 1 month as it is unlikely to change after only 4 weeks of treatment.
  - 3, 6 and 9 months: safety visit (basic chemistry panel, adverse event assessment, GI symptoms questionnaire, BP, pill compliance).
  - 6 months: in addition to the safety visit, outcome measures: FMDBA, aPWV, plasma AII, aldosterone, ET-1 and serum T50 and 24-hour urine collection.

- 12 months: 1) Adverse event assessment, GI symptoms questionnaire, BP, pill compliance; 2) outcome measures: FMDBA, aPWV, LVMI, serum basic chemistry panel, plasma AlI, aldosterone, ET-1, serum T50, venous blood gas, and 24-hour urine collection.

**4. Study Drug Dosing.** The study drugs (bicarbonate and the matched placebo) will be prepared by Belmar Pharmacy and will be identical in size, color, shape and taste. Each sodium bicarbonate capsule contains 7.7 mEq of bicarbonate and 178 mg of sodium. The matching placebo capsule will contain cornstarch. Belmar Pharmacy will bottle the capsules and label the bottles with code numbers to maintain the study's double blind and ship the bottles directly to the investigative site.

**a) Sodium bicarbonate:** Subjects randomly assigned to sodium bicarbonate therapy will receive 0.5 mEq/kg-lean body weight (LBW)/day for the entire 12 months. Participants will take ½ the daily dose in the morning and the other ½ in the evening. The number of capsules will be rounded to the nearest whole capsule. To reduce pill burden and increase compliance the maximum number of pills per day will be six.

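### The study statistician generates the randomisation list yet is stated to stay blinded until the final analysis, and no described procedure secures that blind

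*Combined protocol and SAP*

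**What the plan says.** Three statements in the combined protocol and SAP bear on this.

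- **Section IV.A, Rigorous Experimental Design, Randomization.** The method is stated as follows: "Participants will be randomized with a 1:1 allocation ratio to treatment and placebo group using block randomization". On the list itself: "List of randomization will be generated by the study statistician and sent to the study pharmacist". The only person from whom the list is said to be withheld is the principal investigator.
- **Same paragraph, on who is blinded.** "Study investigators, healthcare providers, participants, data collectors, outcome adjudicators and data analysts will be blinded to treatment assignment". The study statistician is not named here, though data analysts are.
- **Protection of Human Subjects, item 5, Data and Safety Monitoring Plan.** "The data will be prepared by the DSMB statistician, ensuring the study statistician remains blinded until the final analysis". The same plan has the DSMB "reviewing unblinded data for safety".

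Two further provisions mention codes. Under Study Drug Dosing (item 4), the pharmacy will "label the bottles with code numbers" and ship the bottles to the site. Under Adequacy of Protection Against Risks, b), the confidentiality arrangement reads: "Only the PI and Study Coordinator will maintain the code linking study identification numbers to specific participants".

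**The concern.** One role title is used for two functions that do not sit together without a further safeguard. The study statistician writes the sequence of treatment assignments, and the study statistician is declared blind to assignment until the end. Someone who generates a list cannot be presumed blind to it, and the plan gives no reason why this person would be.

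What is at stake is the credibility of a claim the trial will want to make in its report, namely that its statistician was blinded. The sponsor evidently values that claim, since a separate statistician prepares the DSMB data in order to protect it. The claim carries weight because parts of the analysis are not yet fixed. Choices made by someone who could know the arms do not have the protection the plan says they have.

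**Working it through.** No arithmetic applies. The check sets the provisions side by side and asks whether any of them keeps the list from its author.

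**1. Does a safeguard elsewhere close the gap?**

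| Provision | What it protects | Masks the list from its author? |
|---|---|---|
| DSMB statistician prepares the monitoring data | Accumulating results by arm | No. It closes a different route |
| Pharmacy code numbers on bottles | Site staff and participants handling the capsules | Not stated |
| Code linking study number to person | Participant identity | No. It is not a treatment code |
| List withheld from the principal investigator | The principal investigator | No |
| Statement that data analysts are blinded | An intention, with no mechanism given | No |

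Masked arm labels, sealing of the list after generation, and a second person who holds the key are not mentioned anywhere.

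**2. What would the statistician need in order to know a participant's arm?** Two things: the list, and a link from list position or bottle code to study number. The documents say the statistician produces the first. They do not say whether it is retained, and they are silent on who can see the second. If bottle numbers follow list order and the bottle number or order of randomisation is in the dataset, the link is easy to make. If not, it may be unavailable. That condition is an assumption either way.

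**3. Which analysis choices remain open?**

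- Section 11, Descriptive statistics: highly skewed variables may or may not be transformed.
- Section 11, General consideration: multiple imputation is announced without a model, and sensitivity analyses are only partly specified. The ANCOVA covariates are not listed.
- Section 9, a) Primary Outcomes: flow-mediated dilation will be adjusted for shear rate if groups or conditions differ, with no rule for what counts as a difference.
- Section 12: blood pressure will be adjusted for if control differs between groups, again without a rule.

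The Section 11 choices can be settled on pooled data without allocation, so a real blind protects them directly. For the shear and blood pressure adjustments, the triggering rule can be written in advance, but applying it needs data grouped by arm.

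**4. What does resolving the point change numerically?** Nothing. The planned 54 per group, the stated power and the 0.025 level for each primary outcome do not depend on who makes the list.

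**The case against.** The strongest reply is that the two statements can be reconciled. Generating a list is not the same as keeping it, and participant-level knowledge also needs the link to study number, which no passage gives the statistician. The monitoring sentence can also be read narrowly, as saying only that DSMB preparation will not unblind the study statistician. Much of this stands. A reader might infer that the statistician holds every participant's allocation from the start, or that the two statements cannot both be true. The documents do not support that: an undescribed safeguard could make them compatible. What the reply does not supply is the safeguard itself. Even on the narrow reading, the sentence still asserts blindness up to the final analysis.

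A second reply is that no passage assigns the analysis choices to the study statistician. That is correct. It is a natural inference from the role and from the reference to the final analysis, but it remains an inference. The statement that "outcome adjudicators and data analysts will be blinded to treatment assignment" is contradicted only if the study statistician is one of those analysts.

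A third reply concerns harm. The primary analysis is fixed in outline (intention to treat, complete-data ANCOVA of 12-month change, 0.025). The two between-group adjustments need grouped data whoever made the list. Fitting parametric curves belongs to the additional longitudinal analysis, not to the primary test. All of this stands. A reader might go on to attach an inflated error rate to the defect, but that would measure selective reporting among several analyses, which can occur after unblinding whoever held the list. It is a consequence of incomplete pre-specification, not of this inconsistency.

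Finally, the monitoring plan describes the study as not firmly confirmatory. That lowers the stakes, but a blinding statement in the protocol should still be true.

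**Conclusion.** The concern holds in a limited form. As written, the procedure does not secure the blind that the Data and Safety Monitoring Plan asserts for the study statistician, and the two passages need reconciling. The conclusion rests on two things: the same role title being used in both places, and the absence of any described masking, sealing or key-holding arrangement. It does not rest on, and the documents do not establish, actual unblinding of the statistician or any effect on the results.

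The direction and size of any bias cannot be estimated from the documents. The practical consequence is for credibility: as long as the text stands, a report that the study statistician was blinded could be challenged from the protocol itself. It should be corrected, and the correction is cheap.

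**What to change.** Amend the Randomization paragraph of Section IV.A in one of two ways, and align the sentence in the monitoring plan with it.

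1. The study statistician supplies only the specification (1:1, blocks). The DSMB statistician, who already prepares data for a board that reviews them unblinded, generates the list with a seed the study statistician does not hold and sends it to the pharmacy.
2. The list is generated with masked arm codes, and only the pharmacy and the DSMB statistician hold the key.

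The first is the more robust. Under the second, mean serum bicarbonate by coded group at follow-up could suggest which code is active.

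Under either option, state that the study statistician receives the allocation only after database lock, and after the transformation rule, imputation model, ANCOVA covariates and the triggers for shear and blood pressure adjustment are fixed in writing.

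If the list has already been issued, disclose who generated it and who has had access, and have an analyst without access to the allocation fix the remaining choices. That analyst should not be the DSMB statistician, who works with unblinded data. If a safeguard already operates in practice, describing it is enough.

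The cost is a sentence or two of protocol text and, under the first option, one task moved to a role the plan already has. Only the already-issued case might need time from an additional analyst.
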